## **Intervention Groups and Duration:**

Arm Name	Intervention Name	Unit Dose Strength(s)	Dosage Level(s)	Route of Administration	Regimen/ Treatment Period/ Vaccination Regimen	Use
MK-2060	MK-2060	15 mg/mL	30 mg	SC	Part 1: Day 1 Part 2: Days 1, 2, 3, 4, 8, 15, and 22 Part 3: Day 1	Test Product
Placebo	Placebo	Saline	0 mg	SC	Part 1: Day 1 Part 2: Days 1, 2, 3, 4, 8, 15, and 22	Placebo

SC=subcutaneous; USP=United States Pharmacopeia

08V5WO

Placebo SC (0.9% sodium chloride infusion, USP sterile saline)

Total Number of Intervention Groups/Arms	There will be 3 intervention groups.
Duration of Participation  Duration of Participation	Part 1: Each participant will participate in the study for approximately 19 weeks from the time the participant provides documented informed consent through the final contact. After a screening phase of 4 weeks, each participant will receive assigned intervention for approximately 1 day. After the end-of-treatment each participant will be followed for approximately 13 weeks.  Part 2: Each participant will participate in the study for approximately 20 weeks from the time the participant provides documented informed consent through the final contact. After a screening phase of 4 weeks, each participant will receive assigned intervention for approximately 4 weeks (4 consecutive days of loading doses followed by weekly single dose x 3). After the end-of-treatment each participant will be followed for approximately 13 weeks.  Part 3: Each participant will participate in the study for approximately 23 weeks from the time the participant provides documented informed consent through the final contact. After a screening phase of 4 weeks, each participant will receive assigned intervention for approximately 1 day. After the end-of-treatment each
	participant will be followed for approximately 17 weeks.

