Spot Urine Collection for Urine Protein: Urine Creatinine Ratio			X											X				X				If a participant is unable to produce a urine sample at Day 1 12-hours postdose, this spot urine can be collected the next time the participant is able to void. Sec. 8.3.4, Appendix 2.
Hematology, Chemistry, Urinalysis	X	X d	X			X	X		X		X		X	X		X		X	X		X	Hematology/Chemistry/Urinalysis will be obtained after an 8-hour fast. Days 1, 8, 15, and 22 samples will be predose. Sec. 8.3.5, Appendices 2 and 8.
aPTT and PT at local lab	X		X			X	X		X		X		X	X							X	Days 1, 8, 15, and 22 samples will be predose. Sec. 5.2, 8.3.5, Appendices 2 and 8

												Part 2	2									
	≤28	eening 8 days Day 1			Intervention									Post- study	Notes							
Scheduled Timing (Week)	Screening 1	Screening 2a		We	ek 1		We 2		We		W	∕ eek ⁴	4			Pos	t W	eek	4			
Scheduled Timing (Day)			1	2	3	4	8	10	15	17	22	23	26	29	35	42	49	63	81	111	130	
Visit Window (Day)			NA	NA	NA	NA	NA	±1	NA	±1	NA	NA	±1	NA	±2	±2	±2	±2	±3	±3	±7	
Hemoccult test	Xe			X		X	X	X	X	X	X	X		X	X	X	X	X	X	X		Sec. 8.3.6.
Biomarkers																						
Blood for Genetic Analysis f			X																			Collected predose from enrolled participants only. Sec. 8.8.1, Appendix 8
Pharmacokinetics																						
Blood for Plasma MK-2060			X	X		X	X	X	X	X	X		X	X	X	X	X	X	X	X	X	Days 1, 2, 4, 8, 15, and 22 samples will be predose. Sec. 8.6.1, Appendix 8, and Study Operations Manual
Pharmacodynamics																						
Blood for PT/aPTT/FXI activity by central lab			X	X		X	X	X	X	X	X		X	X	X	X	X	X	X	X	X	Days 1, 2, 4, 8, 15, and 22 samples will be predose. Sec. 8.7.1, Appendix 8, and Study Operations Manual
Blood for Plasma ADA			X						X		X						X	X	X	X	X	Days 1, 15 and 22 samples will be predose Sec. 8.7.2, Appendix 8, and Study Operations Manual

	r											Part 2	2									
	≤23	eening 8 days Day 1								Int	erve	ntion	l								Post- study	Notes
Scheduled Timing (Week)	Screening 1	Screening 2 a		We	Veek 1 Week 2 Week 4 Post Week 4																	
Scheduled Timing (Day)			1	2	3	4	8	10	15	17	22	23	26	29	35	42	49	63	81	111	130	
Visit Window (Day)			NA	NA	NA	NA	NA	±1	NA	±1	NA	NA	±1	NA	±2	±2	±2	±2	±3	±3	±7	

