## 4.2.1.2 Pharmacokinetic Endpoints

#### Plasma PK of MK-2060

In order to characterize the PK profile of MK-2060 PK in adults with CKD and ESKD, noncompartmental PK parameters including AUC0-∞, AUC0-168, Cmax, C168, Tmax, terminal t1/2, CL/F, and Vz/F will be summarized after single- and multiple-dose SC administration.

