### 4.3 Justification for Dose

As this is a Phase 1 assessment of MK-2060 in humans, and the PK, pharmacodynamic and safety profiles of the compound are still being evaluated, modifications to the dose or dosing regimen may be required to achieve the scientific goals of the study objectives and/or to

ensure appropriate safety monitoring of the study participants. Details of allowed modifications are provided in Section 8.11.6.

For Part 1, the 30-mg single SC dose was selected, because, from preliminary modeling and simulation analysis, this dose is anticipated to provide a maintenance level of aPTT prolongation at steady state via QW SC dosing in at least of CKD4 patients. The 30-mg single SC dose of MK-2060 is anticipated to result in a geometric mean Cmax of approximately and AUC0-∞ of 11300 nM\*hr. These numbers are based upon preliminary population PK modeling of observed PK of single SC doses in P001 and observed PK in ESKD-HD participants in P004. The projected exposures assume a bioavailability observed in SC dosing of MK-2060 in P001 NHV (SC/IV GMR for AUC0-∞ and AUC0-last were respectively), and a t1/2 observed in ESKD-HD patients after IV administration (P004, CCI).

These exposures are significantly lower than the chronic toxicology NOAEL (Cmax approximately AUC0-168 = from the 4-week rhesus monkey toxicity study at 60 mg/kg/week). In P004 (Part 2), where ESKD-HD patients received multiple QW 25-mg doses of MK-2060, the observed geometric mean steady state Cmax and AUC0-168 was approximately and GCI and GCI respectively, and MK-2060 was generally well tolerated.

In Part 2, preliminary analysis of PK and pharmacodynamic data from Part 1 supports a 30 mg SC dose of MK-2060 to be given as a loading dose for 4 consecutive days, followed by QW doses for 3 weeks. This dosing regimen is anticipated to achieve aPTT prolongation from start of treatment which can be maintained at steady state via QW SC dosing in at least of CKD4 and CKD5 patients. The predicted mean Cmax after last dose of 30-mg SC dose of MK-2060 is CCC. As this dose projection is based on preliminary data from Part 1 together with data from other Phase 1 studies, the dose used may be modified based on additional data.

In Part 3, a single 30 mg SC dose of MK-2060 is proposed based on emerging data from Part 1 and to enable a direct comparison of PK for this dose between CKD4/CKD5 and dialysis patients and the single 30 mg SC dose given to Japanese NHVs in P013.

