#### 8.1.11 Domiciling

08V5WO

For Parts 1 and 3 participants will report to the CRU the evening before the scheduled day of study intervention administration for each treatment period. Participants will remain in the unit until at least 48-hours postdose. For Part 2 participants will report to the CRU the evening before the scheduled day of study intervention administration on Day 1 and will remain in the unit until the completion of off all postdose procedures on Day 4 (at least 4 hours). For the remaining dosing days in Part 2, at the discretion of the investigator the participants will return to the CRU either the evening before the scheduled day of study intervention administration or the morning of the scheduled day of study intervention administration (Days 8, 15 and 22) and will remain in the unit overnight until the completion of all postdose procedures the following day (at least 4 hours). At the discretion of the investigator, participants may be requested to remain in the CRU longer.

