#### 8.11.6 Critical Procedures Based on Study Objectives: Timing of Procedure

For this study, the blood sample for MK-2060 is the critical procedure.

At any post-dose time point, the blood sample for MK-2060 needs to be collected as close to the exact time point as possible. All other procedures should be completed as close to the prescribed/scheduled time as possible. Study procedures can be performed before or after the prescribed/scheduled time.

The order of priority can be changed during the study with joint agreement of the investigator and the Sponsor Clinical Director.

Any nonscheduled procedures required for urgent evaluation of safety concerns take precedence over all routine scheduled procedures.

The following variance in procedure collection times will be permitted.

- Screening 2 procedures: up to additional 4 hours of scheduled time
- PK, Pharmacodynamic and Safety Collection as outlined in Table 7, Table 8, and Table 9.

Table 7 Pharmacokinetic, Pharmacodynamic and Safety (Blood/Urine) Collection Windows for Part1

Pharmacokinetic, Pharmacodynamic, Safety Collection	Pharmacokinetic, Pharmacodynamic Safety Collection Window		
0 to < 4 hours	5 min		
4 - < 8 hours	15 min		
8 - < 24 hours	30 min		
24 hours - < 48 hours	60 min		
48 hours - < 120 hours	2 hours		
120 hours - ≤ 168 hours	24 hours		
Day 11 + Day 14	1 Day		
Day 21	2 Days		
Day 28	3 Days		
Day 60 + Day 90	5 Days		

Table 8 Pharmacokinetic, Pharmacodynamic and Safety (Blood/Urine) Collection Windows for Part 2

Pharmacokinetic, Pharmacodynamic, Safety Collection	Pharmacokinetic, Pharmacodynamic, Safety Collection Window		
0 to < 4 hours	5 min		
Days 1, 2, 3, 4, 8, 15, 22, 23, and 29	No flexible window for the scheduled day		
Days 10 and 17	±1 Day		
Day 26	+1 Day		
Days 35, 42, 49 and 63	±2 Days		
Days 81 and 111	±3 Days		
Day 130	±7 Days		

Table 9 Pharmacokinetic, Pharmacodynamic and Safety (Blood/Urine) Collection Windows for Part 3

Pharmacokinetic, Pharmacodynamic, Safety Collection	Pharmacokinetic, Pharmacodynamic, Safety Collection Window		
0 to < 4 hours	5 min		
4 - < 8 hours	15 min		
8 - < 24 hours	30 min		
24 hours - < 48 hours	60 min		
48 hours - < 120 hours	2 hours		
120 hours - ≤ 168 hours	24 hours		
Day 11 + Day 14	1 Day		
Day 21	2 Days		
Day 28	3 Days		
Day 60 + Day 90 + Day 120	5 Days		

- Part 1, 2, and 3 Day 1 predose standard safety evaluations: VS and ECG at 3 hours; laboratory safety tests and physical exam at 24 hours

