#### 9.4 Analysis Endpoints

#### **Primary Endpoints**

- 1. Primary endpoints are bleeding related AEs, AEs, and discontinuations due to AEs.
- Pharmacokinetics: The pharmacokinetic variables of primary interest for MK-2060 are measurement of MK-2060 plasma AUC0-∞, AUC0-168, Cmax, C168, Tmax, terminal t1/2, CL/F and Vz/F

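### After the last Part 2 dose the only PK sample before 168 h is at a nominal 96 h, so last-dose Tmax is fixed by the grid and Cmax and AUC0-168 read somewhat low; one Day 23 draw would limit this cheaply

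*Combined protocol and SAP*

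**What the plan says.** Doses are given on "Part 2: Days 1, 2, 3, 4, 8, 15, and 22" (Section 1.1, Intervention Groups and Duration). The row "Blood for Plasma MK-2060" in Section 1.3.2 marks Days 1, 2, 4, 8, 10, 15, 17, 22, 26, 29, 35, 42, 49, 63, 81, 111 and 130. Its note says "Days 1, 2, 4, 8, 15, and 22 samples will be predose", so the Day 22 sample is the trough before the last dose. Day 23 is a visit, but the schedule gives it only the local injection-site check and the hemoccult test.

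Section 9.4 names as the PK variables of primary interest "measurement of MK-2060 plasma AUC0-∞, AUC0-168, Cmax, C168, Tmax, terminal t1/2, CL/F and Vz/F". Section 4.2.1.2 calls these noncompartmental and says they "will be summarized after single- and multiple-dose SC administration". Section 4.3 refers to "The predicted mean Cmax after last dose of 30-mg SC dose of MK-2060"; the value is not legible in the public text.

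After the Day 8, 15 and 22 doses, participants "will remain in the unit overnight until the completion of all postdose procedures the following day" (Section 8.1.11). Table 8 in Section 8.11.6, which gives PK, PD and safety collection windows, includes in its no-flexibility row "Days 1, 2, 3, 4, 8, 15, 22, 23, and 29". It gives Day 26 a window of plus 1 day, where the schedule gives plus or minus 1 day.

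**The concern.** A noncompartmental Cmax is the largest value observed, and Tmax is the time of that value. If the true peak falls between 0 and 96 h, the grid cannot show it. Tmax then reports the schedule rather than the drug, and Cmax can only be too low. A trapezoid drawn straight from trough to the 96 h value cuts off the rise and the peak, so AUC0-168 is low as well.

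The last-dose interval is the one for which Section 4.3 projects a Cmax, so a reader is likely to set the observed value beside that projection. C168 is not affected, because Day 29 is sampled at 168 h.

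**Working it through.** **1. Sampling times after the last dose.** Day 22 predose = 0 h; Day 26 = (26 - 22) x 24 = 96 h; Day 29 = (29 - 22) x 24 = 168 h. A Day 23 draw would be at 24 h.

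**2. Is the Day 23 blank real?** Appendix 8 lists 8 collections for ADA plus MK-2060 and 9 for MK-2060 only, so 17. The schedule row also has 17 marks. The volumes reproduce:
- Male: 13 x 12.5 + 5 + 8.5 + 8 x 2.7 + 9 x 3 + 17 x 10 + 9 x 1.8 = 410.8 mL.
- Female: 410.8 + 3.5 + 14 = 428.3 mL.

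Both match Appendix 8. The blank is therefore intended and not a fault of text extraction.

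**3. Model (assumed).** One compartment, first-order absorption, linear kinetics, equal doses at 0, 24, 48, 72, 168, 336 and 504 h:

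C(t) = sum over doses d <= t of ka/(ka - ke) x [exp(-ke(t - d)) - exp(-ka(t - d))], with ke = ln 2 / half-life.

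The dose scale cancels. The grid is half-life 5, 7, 10, 15, 20 days by ka 0.2, 0.3, 0.5, 0.8 per day, giving 20 scenarios. Dense-grid Cmax and AUC over 504 to 672 h are compared with the scheduled samples by linear trapezoid.

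**4. Two scenarios worked through.**
- Half-life 10 days, ka 0.5. C at 0, 24, 96, 168 h = 2.324, 2.559, 2.506, 2.131; true peak 2.625 at 50 h; true AUC 412.9. Cmax: 2.506/2.625 - 1 = -4.5%. AUC: 96 x (2.324 + 2.506)/2 + 72 x (2.506 + 2.131)/2 = 398.8, so -3.4%. With the 24 h draw: Cmax 2.559/2.625 - 1 = -2.5%; AUC 407.9, so -1.2%.
- Half-life 5 days, ka 0.8 (worst case). C = 0.956, 1.343, 1.197, 0.818; true peak 1.403 at 42.5 h; true AUC 197.0. Cmax: 1.197/1.403 - 1 = -14.7%. AUC: 175.8, so -10.7%. With the 24 h draw: Cmax -4.3%, AUC 191.5, so -2.8%.

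**5. All 20 scenarios.** True Tmax after the Day 22 dose is 43 to 86 h.

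| Samples (h) | Cmax bias, range (median) | AUC0-168 bias, range (median) | Observed Tmax (h) |
|---|---|---|---|
| 0, 96, 168 (as planned) | -0.1% to -15% (-4.1%) | -0.9% to -11% (-2.6%) | 96 in all |
| 0, 24, 96, 168 (Day 23 added) | -0.1% to -4.5% (-2.0%) | -0.5% to -2.8% (-1.0%) | 24 or 96 |

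If Day 26 falls at 72 h, which the schedule allows, Cmax bias is 0 to -5.8%. If it falls at 120 h, which both places allow, Cmax bias is -0.6% to -24% and AUC0-168 bias -1.4% to -16%. In 5 of the 20 scenarios the predose trough then becomes the observed maximum.

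**6. Dependence on the assumed grid.** A wider grid (single-dose Tmax 24 to 168 h, half-life 5 to 28 days) gives Cmax bias -0.3% to -32.9% and AUC0-168 bias -1.7% to -19.7%. With a 24 h draw these become -0.3% to -4.6% and -0.7% to -2.8%. The direction is the same throughout; the size is not fixed by the documents.

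**7. Yardstick.** Section 9.6 expects a CV of about 30% for AUC0-infinity. The log-scale SD is sqrt(ln(1 + 0.3^2)) = 0.294. With n = 9 the standard error of a geometric mean is 0.294/3 = 0.098, about 10%.

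**The case against.** Several points on the other side stand.

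- **Table 8.** A reader might infer that Table 8 proves a planned Day 23 PK sample was lost. It does not. Its fixed-day list is exactly the set of schedule days whose visit window is NA, and it includes Day 3, which has no blood or urine draw either. It looks like a carried-over list of visit days. The schedule and Appendix 8, which do specify draws, agree on 17.
- **Days 10 and 17.** Each gives a nominal 48 h sample after a weekly dose. In the same model the Day 17 sample lies within about 2.5% of the true peak of its interval in every scenario, so near-peak concentrations under weekly dosing are seen. The plan does not say that Part 2 parameters come only from the Day 22 interval. These samples do not, however, describe the interval after the last dose.
- **Contrast with Part 1.** Part 1 has no sample between 48 h and 120 h. Its AUC0-168 bias in the same model is -2.2% to -3.6% (median -2.9%), at least as large as that of Part 2 in 11 of 20 scenarios. Its Cmax bias reaches -5.4%. Part 1 is not a clean reference.
- **Use of the results.** Part 2 is for estimation with descriptive statistics. No test of observed against predicted Cmax is planned.
- **Flexibility.** Section 8.11.7 lets the sampling scheme change to get closer to the peak. That permits a sample but does not plan one.
- **Reach of the remedy.** The modelled Tmax is 43 to 86 h, so a 24 h draw does not recover it.

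**Conclusion.** The gap is real but modest. In the last-dose interval, Tmax is the firm loss: its nominal value can be only 0, 96 or 168 h, and the modelled true value is missed in every scenario. Cmax and AUC0-168 are biased low in all 20 scenarios, typically by about 4% and 2.6%, and by up to 15% and 11% when half-life is short and absorption fast. In many scenarios this is small beside the 30% CV and the roughly 10% standard error at n = 9, although a bias does not average out.

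The size rests on an assumed linear one-compartment model, which ignores any target-mediated disposition, and on assumed half-life and absorption ranges. The documents do not support saying that the primary PK results are seriously distorted or that a planned sample was dropped. The point is a cheap improvement, not a flaw that undermines Part 2.

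**What to change.** Add an MK-2060 plasma draw to the existing Day 23 visit at 24 h after the Day 22 dose, while participants are still in the unit. State that Part 2 last-dose Tmax is limited by the sampling grid.

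The cost is one 1.8 mL sample per participant: 410.8 + 1.8 = 412.6 mL for men and 428.3 + 1.8 = 430.1 mL for women. Central PD blood accompanies every other Part 2 PK draw. Keeping that pairing adds 10 mL more, giving 422.6 and 440.1 mL. Both options are smaller than the extra 50 mL allowed in Section 8.11.7. Because the draw would be planned, the Part 2 maximum in Section 8 and the totals in Appendix 8 should be updated rather than using that contingency.

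As separate housekeeping, reconcile Table 8 with the schedule: Days 3 and 23 are listed without a draw, and the Day 26 window differs. A line saying that noncompartmental analysis uses actual sampling times would also help, given the width of that window.

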#### 2 INTRODUCTION

## 2.1 Study Rationale

Patients with CKD and ESKD have an increased prevalence of cardiovascular disease, including coronary artery disease, venous thrombosis, atrial fibrillation, and thromboembolic stroke. For patients on hemodialysis, this increased risk of thrombotic events also carries a high rate of vascular access thrombosis, particularly in those with AVGs where it can lead to access failure. Anticoagulants are therefore commonly used in this patient population. However, these patients also have an increased risk of bleeding events, which needs to be balanced with the increased risk of thrombotic events using currently marketed anticoagulants.

MK-2060 is an anti-FXI monoclonal antibody being developed for the prevention of thrombotic complications in CKD and ESKD. In contrast to most current anticoagulants, the use of agents that inhibit FXI are expected to reduce the risk of thrombotic events while having minimal effect on hemostasis. Hence, targeting FXI is an attractive option to expand the therapeutic window for anticoagulation in CKD and ESKD patients. The purpose of this study is to evaluate the safety, PK and pharmacodynamics of a single and multiple SC doses of MK-2060 in participants with Stage 4 and Stage 5 CKD (CKD4 and CKD5), and ESKD on peritoneal dialysis. Characterizing SC dosing in this study will help to broaden the Phase 3 program beyond IV dosing in ESKD patients on hemodialysis, by enabling enrollment of CKD4, CKD5, and ESKD patients with SC injection of MK-2060.

## 2.2 Background

Refer to the IB for detailed background information on MK-2060.

### 2.2.1 Pharmaceutical and Therapeutic Background

FXI is a critical component in the intrinsic pathway of the coagulation cascade. MK-2060 is an anti-FXI monoclonal antibody being developed for the prevention of thrombotic events in CKD/ESKD. Based on preclinical and human genetic data, as well as emerging clinical data using an AS approach [Buller, H. R., et al 2015] [Bethune, C., et al 2017], FXI inhibition is predicted to confer a clinically relevant antithrombotic effect with a reduced risk of bleeding complications and hence an expanded therapeutic index compared to inhibition of more downstream clotting factors such as FXa and thrombin. Therefore, FXI/FXIa inhibition is a promising therapeutic approach for the prevention of thromboembolic events.

#### 2.2.2 Completed Clinical Studies

[figure not shown]
## **Study MK-2060-001:**

Study MK-2060-P001 was a double-blind, randomized, placebo-controlled, single site, sequential panel study to evaluate the safety, tolerability, PK, and pharmacodynamics of single ascending dose administration of SC and IV doses of MK-2060 in healthy male participants. Forty-five healthy male participants received single doses of MK-2060 up to 120 mg administered SC (27 participants) or 40 mg IV (18 participants). MK-2060 was

generally well tolerated and there were no SAEs or discontinuations due to AEs. In healthy male participants single IV doses of 20 mg and 40 mg of MK-2060 resulted in increases in aPTT baseline within 1 hour of administration (FXI activity inhibition), with aPTT remaining baseline for hours.

#### MK-2060-004:

MK-2060-004 was a 2-part, double-blind, randomized, placebo-controlled, multiple-site, sequential-panel, single and multiple dose study in adult male and female ESKD participants on hemodialysis. The study evaluated the safety, PK and pharmacodynamics of IV administration of single-dose (8, 20 or 40 mg) and multiple dose (25-mg loading dose followed by QW dosing for 3 weeks) MK-2060. A total of 38 participants were enrolled. Single doses up to 40-mg and multiple 25-mg doses were generally well tolerated. Two participants discontinued the study due to a drug-related SAE of lower GI hemorrhage (placebo) and nondrug-related AE of COVID-19 infection. A total of 4 SAEs (myocardial infarction, GI hemorrhage, pneumonia, and AV graft thrombosis) were reported in 4 participants (n=1 in MK-2060 group and n=3 placebo group, respectively). The investigator deemed the myocardial infarction as not related to study intervention as the event occurred approximately 11 weeks after the last dose of MK-2060. Intervention-related AEs reported in participants who received MK-2060 included orthostatic hypotension, headache, chromaturia, hematuria, AV fistula hemorrhage, sneezing, and nausea. Anti-drug antibody assessment was positive in 2 participants of which neither participant reported AEs after showing a positive response to MK-2060.

Multiple-dose MK-2060 25 mg showed aPTT prolongation with a maximum mean fold-change of COL . Overall, no effect on PT was observed.

#### MK-2060-008:

MK-2060-008 was a Phase 1, open-label, multi-site multiple-dose study to evaluate the safety and tolerability of coadministered IV MK-2060 and clopidogrel in adult (male and female) participants with ESKD on HD. Following a 14-day run in period, participant on clopidogrel therapy received a loading dose of 25 mg IV of MK-2060 for a total of 3 doses in Week 1 and a single dose of 25 mg IV MK-2060 in Week 2. 12 participants were enrolled in MK-2060, which was generally well tolerated when coadministered with clopidogrel. There were no bleeding related AEs in the study and there was not a significant difference in time to hemostasis following hemodialysis when clopidogrel was administered with or without concomitant administration of MK-2060. Clodipogrel was not shown to impact the PK profile of MK-2060.

